Milestone	Planned date																						
Submission of revised study protocol for PRAC approval	02 April 2024																						
Submission of second revision study protocol for PRAC approval	20 August 2024																						
Submission of third revision of study protocol for PRAC approval	19 December 2024																						
Submission of fourth revision of study protocol for PRAC approval	29 April 2025																						
Submission of fifth revision of study protocol for PRAC approval	11 July 2025																						
Estimated approval of study protocol by PRAC	24 July 2025																						
Registration in the EU PAS register	August 2025																						
Start of data collection	September 2026																						
End of data collection	September 2038																						
Final report of study results	September 2039																						

5 Amendments and updates

None.

6 Milestones

The date of data collection commencement is driven by when efgartigimod is commercially launched in each study country. Efgartigimod has been accessible to patients in the United States (US) since December 2021 and was launched in the European Union (EU) in August 2022.

Milestone	Planned date
Submission of the study protocol for PRAC approval	31 October 2023
Submission of revised study protocol for PRAC approval	02 April 2024
Submission of revised study protocol for PRAC approval #2	20 August 2024
Submission of revised study protocol for PRAC approval #3	19 December 2024
Submission of revised study protocol for PRAC approval #4	29 April 2025
Submission of revised study protocol for PRAC approval #5	July 2025
Estimated approval of study protocol by PRAC	July 2025
Registration in the EU PAS register	August 2025
Start of data collection ¹	September 2026
End of data collection ²	September 2036
Progress report 1 ³	September 2028
Interim report 1 ⁴	September 2030
Interim report 2	September 2032
Interim report 3	September 2034
Interim report 4	September 2036
Interim report 5	September 2038
Final report of study results	September 2039

EU PAS register = European Union electronic Register of Post-Authorisation Studies; PRAC = Pharmacovigilance Risk Assessment Committee.

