¹ Due to the retrospective design of the study, data collection (accrual of data in the datasets) has already occurred prior to access to data. Start and end dates of access to data will differ by study country. Access to data will occur in databases in countries with earliest launch of efgartigimod first (US). For each country, the overall study period will be from the time of efgartigimod launch in that country and will continue for 10 years.

² The end of data collection may vary by country, depending on the start of data collection in the country's database.

³ A progress report will be provided two years after the start of data collection.

⁴ Interim reports will be provided at year 4 (considering the latency period for a malignancy to develop) following the start of data collection, and then every two (2) years through the end of study follow up.

7 Rationale and background

Myasthenia gravis

Myasthenia gravis (MG) is an autoimmune disease caused by immunoglobulin G (IgG) antibodies against postsynaptic antigens at the neuromuscular junction. IgG autoantibodies impair neuromuscular transmission by binding to acetylcholine receptors (AChR), muscle-specific tyrosine kinase (MuSK) or low-density lipoprotein receptor-related protein 4 (LRP4). Approximately 80% of patients with MG have detectable antibodies against AChR. The estimated

prevalence rate for MG is 77.7 per million persons (range 15–179) and the estimated incidence rate (IR) is 5.3 per million person-years (PYs) (range 1.7–21.3) ([Carr 2010](#)).

A considerable variation exists in the management of generalized myasthenia gravis (gMG), and treatment is not standardized. Current treatment options include acetylcholinesterase (AChE) inhibitors, and long-term immune therapies with immunosuppressive agents such as corticosteroids, azathioprine, cyclosporine, and mycophenolate, but tacrolimus, methotrexate, and cyclophosphamide are also used. Thymectomy is also a treatment option for patients with generalised MG. Monoclonal antibodies such as eculizumab, ravulizumab or rituximab are used for more refractory cases ([Vyvgart EPAR](#)). Short term immune therapies such as plasmapheresis/plasma exchange (PLEX) and intravenous immunoglobulins (IVIg) are typically used for treatment of severe exacerbations or refractory cases of gMG in hospital settings ([Vyvgart EPAR](#)).

Background rates of cancer in MG population

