Patient accrual into the study will begin following the launch of efgartigimod (differs by country), allowing for a lag between actual exposure dates and appearance of the medication record/procedure in each of the data sources, and will continue for up to 5 years via database refreshes (assumed to be annual). To achieve a desired sample size across all databases, a minimum of approximately 1,358 patients will be included in the efgartigimod cohort and 2,716 matched patients in the reference cohort. Accrual of patients into the study cohorts will be monitored annually. Patients will be followed from study entry to at least 10 years following inclusion in the study. If efgartigimod uptake is slower than expected, patient accrual may need to be extended to reach the required sample size.

² CCI is a method of predicting mortality by classifying or weighting comorbid conditions and has been widely utilized by health researchers to measure burden of disease and case mix. Nineteen (19) conditions are included in the index. Each condition is assigned a weight from 1 to 6, based on severity of the disease and estimated 1-year mortality, and these weights from the comorbidities were added to give a singular numeric score which will act as a way of quantifying current health status.

The study will assess the occurrence of any malignancy according to International Classification of Diseases, Tenth Revision (ICD-10) diagnosis codes, which will be grouped according to the ICD-10 classification system (or to the ICD revision valid at time of analysis). More specifically, the first incidence of and time to any malignancy (incidence rate of events of malignancy per PYs exposed in the efgartigimod treated cohort compared to the reference cohort), as well as incidence rate ratio (IRR) will be estimated.

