9.2.2 Study observation period

The first interim report will be submitted to the European Medicines Agency (EMA) at year 4 following the start of data collection, and then will be submitted on a biennial basis (i.e., five interim reports in total for the entire study period). Each patient selected will be followed from his/her respective index date until the earliest occurrence of:

[figure not shown]
- Loss to follow-up (i.e., patient no longer covered in the data source)
- Death (NOTE: The approach for evaluation of death outside of a hospital setting will differ by database)
- End of study follow-up period (10 years after the last patient selected per database)

The cohorts are considered to have dynamic inclusion periods. At each interim analysis, the cohort populations and patient matching will be redefined. Patients in the reference cohort who have switched from any other MG treatment to efgartigimod will be considered as having

³ Only new users of efgartigimod will be included in the efgartigimod cohort, that is, patient who receives a first prescription, or dispensing, or has a procedure code for efgartigimod during the study period, and without a prescription or dispensing or a procedure code for efgartigimod in the previous 12 months.

reached the end of their follow-up period at the time of the switch and will thus be censored from the reference group but counted in the efgartigimod group.

Figure 1. Study observational period

9.2.2.1 Switch from reference cohort to efgartigimod cohort or multiple cumulative exposure to efgartigimod during study period

It is anticipated that during the study period, patients who are in the reference cohort at study entry may initiate efgartigimod at a later time; or patients who are in the efgartigimod cohort at study entry may reinstate efgartigimod a long time following their index exposure.

Details on handling patients who switch therapies or with multiple cumulative exposure to efgartigimod is briefly described in section 13 Data analysis and will be elaborated in the SAP.

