It is anticipated that 829 and 681 cumulative efgartigimod-treated patients in UK and France up to year 2028, and 90% and 100% will be captured in the CPRD and SNDS databases, respectively. 1200 patients are anticipated in Optum database. Factors that may decrease the number of patients in the final analysis include inclusion/exclusion criteria, lost to follow-up, failure to match

to reference, no malignancy history in the look-back period, etc. Therefore, 30% of the patients in CPRD or SNDS are assumed to be excluded from the final analysis, and this percentage increases to 50% in Optum owing to higher loss-to-follow-up rate and shorter look-back period. A total of 1,599 efgartigimod-treated patients combining all 3 databases are anticipated to be included in the final analysis, which is greater than the sample size calculated above. Therefore, it is feasible to have sufficient efgartigimod-treated patient and achieve satisfactory power in the analysis.

Table 5. Anticipated efgartigimod-treated patients included in the final analysis

Database (Country)	Cumulative Patients by Country	% Captured in Database	Projected Patients in Database	% Included in Study	Sample Size in Each Database	Total Sample Size
CPRD (UK)	829	90%	746	70%	522	1,599
SNDS (France)	681	100%	681	70%	477	
Optum (US)	-	-	1,200	50%	600	

Abbreviations: CPRD = Clinical Practice Research Datalink; SNDS = le Système National des Données de Santé; UK = United Kingdom; US = United States.

12 Data management

Data management will be in accordance with the Sponsor’s designated contract research organisation (CRO)’s standard operating procedures (SOPs) regarding external data management which outline the procedures for establishing a data agreement, conducting a data intake analysis, performing data load and verification, executing data backups, defining data retention and destruction timelines. Additional SOPs may be applicable depending on the format of the data files to be delivered by the providers.

Furthermore, data protection and privacy procedures will be followed to ensure data files received from providers are processed for specific study purposes and only those requiring data access will have access to the data. This also ensures data are accurate and not kept longer than needed, and defines logical and physical data security standards which meet regulatory guidelines. Data transferred from the providers will be stored in a dedicated application instance for the MAH.

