18.2 Collection of adverse events

Although AE information is not being actively solicited via this protocol, all ADRs that are inadvertently discovered and has an identifiable patient must be reported to argenx by email or fax.

Email: [contact]

[contact]

One or more of the following qualifies a patient as identifiable: sex, age [or category, for example “elderly”], date of birth, initials, hospital, or other identifying item. In order for an event to be classified as an ADR, the database medical record should clearly indicate that the treating physician considered there to be a possible causal relationship between the AE and efgartigimod.

19 Plans for disseminating and communicating study results

Registration in the ENCePP register is planned. A progress report will be provided two (2) years after the start of data collection, which will present information on enrolment in the study cohorts, overall and by country (i.e., database). Interim results will be provided at year four (4) following the start of data collection, and then will be submitted on a biennial basis to the EMA; and a final study report will be provided one (1) year after the end of data collection if additional time is required to meet enrolment numbers to the EMA and to the competent authority of each country where the study is being conducted.

20 References

- (2) Bhavaraju-Sanka R. (2024, February 22-23). Patterns of efgartigimod dosing in clinical practice in the United States [Conference presentation abstract]. Forty-sixth Annual Carrell-Krusen Neuromuscular Symposium. Dallas, TX, United States.

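### The protocol's end-of-follow-up rules cannot all hold, and the choice between them moves the administrative censoring date by up to about 6.1 (EU) to 6.75 (US) years

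*Protocol*

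**What the plan says.** The protocol fixes the end of follow-up in five places.

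- **Section 6, footnote 1:** for each country, "the overall study period will be from the time of efgartigimod launch in that country and will continue for 10 years". The same section says efgartigimod has been "accessible to patients in the United States (US) since December 2021 and was launched in the European Union (EU) in August 2022".
- **Section 9.2.2:** one of the events that end a patient's follow-up is "End of study follow-up period (10 years after the last patient selected per database".
- **Section 9.1 (and the abstract):** "Patients will be followed from study entry to at least 10 years following inclusion in the study". Accrual starts after launch and "will continue for up to 5 years via database refreshes (assumed to be annual", with extension allowed if uptake is slow.
- **Abstract, milestone table:** the row "End of data collection" reads September 2038.
- **Section 6, milestone table:** the same row reads September 2036. That table also lists interim report 5 in September 2038 and the final report in September 2039.

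Three further places bear on the point. Footnote 2 lets the end of data collection differ between countries. Section 11 bases feasibility on "cumulative efgartigimod-treated patients in UK and France up to year 2028". Section 19 says that "a final study report will be provided one (1) year after the end of data collection", followed by a condition about needing extra time to meet enrolment numbers.

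**The concern.** A launch-based end and an end counted from the last patient are different rules. Under footnote 1 only a patient who enters on launch day can reach ten years, so it also conflicts with the minimum in section 9.1. The two milestone tables then give two single dates for one milestone, and the section 6 table places an interim report two years after its own end of data.

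This is more than a clerical slip. Section 13.2 stops person-time in the primary as-treated analysis at the end of the study period, and section 13.4 does the same for the intention-to-treat analysis. The rule therefore decides which events and person-years are counted. The years at risk are the late ones, which matter most here: section 15 puts cancer latency at 2 years to decades and names risk at 5 or more years after initiation as hard to evaluate. A SAP could not settle the matter without overriding one of the protocol's statements.

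**Working it through.** **Inputs.** Launch December 2021 (US) and August 2022 (EU), section 6; no UK launch date is given. Accrual up to 5 years (section 9.1), or to 2028 (section 11, read here as end 2028). Follow-up 6 or 8 years, rate ratio 1.3, two-sided 5% test, background rate 42.0 per 1,000 person-years, inflation factor 2, N = 1,358 (section 11). Matching is 2:1 (section 9.1).

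**Step 1: the plan's own figure.** For a Wald test on the log rate ratio, the variance per efgartigimod patient is 1/(t·λ1) + 1/(2·t·λ0), with λ0 = 0.042 and λ1 = 1.3 × 0.042 = 0.0546.

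- t = 6: 1/0.3276 + 1/0.504 = 3.0525 + 1.9841 = 5.0366. With 1,358/2 = 679 effective patients, SE = √(5.0366/679) = 0.0861. Power = Φ(0.2624/0.0861 − 1.96) = 86.13%, as stated in Table 4.
- t = 8: the same formula gives 94.03%, also as stated.

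The sample size arithmetic is sound for the follow-up it assumes.

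**Step 2: end date under each rule** (mid-month dates; gap in years from footnote 1).

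| Rule | US end (gap) | EU end (gap) |
|---|---|---|
| Footnote 1: launch + 10 | Dec 2031 | Aug 2032 |
| Section 6 table | Sep 2036 (4.75) | Sep 2036 (4.08) |
| 9.2.2, 5-year accrual | Dec 2036 (5.0) | Aug 2037 (5.0) |
| Abstract table | Sep 2038 (6.75) | Sep 2038 (6.08) |
| 9.2.2, accrual to end 2028 | Dec 2038 (7.04) | Dec 2038 (6.38) |

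**Step 3: potential follow-up of the last entrant** (before death or loss).

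| End date | 5-year accrual, US / EU | Entry at end 2028, US / EU |
|---|---|---|
| Footnote 1 | 5.0 / 5.0 | 2.95 / 3.62 |
| September 2036 | 9.75 / 9.09 | 7.71 / 7.71 |
| September 2038 | 11.75 / 11.09 | 9.71 / 9.71 |

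Footnote 1 and September 2036 both miss the ten-year minimum under either accrual window. September 2038 meets it for anyone entering by September 2028.

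**Step 4: mean maximum follow-up under footnote 1,** assuming uniform accrual: (longest + shortest)/2.

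- 5-year accrual: (10 + 5)/2 = 7.5 years.
- Accrual to end 2028: (10 + 2.95)/2 = 6.5 years (US); (10 + 3.62)/2 = 6.8 years (EU).

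All lie below 8 years and above 6.

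**Step 5: power at those means** (Step 1 formula, N = 1,358): 93% at 7.5 years and 89% at 6.5 years. At 5 years it would be 79%.

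**The case against.** The strongest reply is that most of the protocol points one way. Section 9.2.2 is the operative censoring rule, and the ten-year minimum in section 9.1 follows from it. The abstract date, interim report 5 and the September 2039 final report all sit at or after 2038. On this view the outliers are one footnote and one table cell, and the repair is short. That is a fair account of what was probably meant, and it is why the remedy is cheap. It does not remove the conflict: footnote 1 states a country-level study period in plain terms, and footnote 2 explains neither two single dates for one milestone nor the difference between launch + 10 and last patient + 10.

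Several stronger readings are tempting and are not supported.

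- **The sample size fails.** A reader might infer that footnote 1 pushes mean follow-up below the 6 years behind 1,358. This needs an annual loss rate that the documents do not state. With 5% per year (an assumption) and EU accrual to end 2028, the mean is about 5.7 years and power about 84%. With the same loss and a 5-year accrual, the mean is 20 × [1 − (e^−0.25 − e^−0.5)/0.25] = 20 × (1 − 0.689) = 6.2 years, so the shortfall vanishes. Section 11 also already removes 30% or 50% of patients, partly for loss, and projects 1,599 rather than 1,358.
- **Interim reports 3 to 5 would add no follow-up under footnote 1.** Section 9.1 allows for a recording lag and annual refreshes, so a 2034 report could still add data, and the UK launch date is unknown.
- **Accrual must end by 2027, against the 2028 projection.** Launch differs by country, and section 9.1 permits extension.
- **Section 19 proves the 2038 date.** The one-year interval there carries a condition about enrolment, so it is only supportive.

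**Conclusion.** The contradiction is in the current text and needs correcting before data collection starts in September 2026. Between footnote 1 and the abstract's date, the administrative end moves by 6.75 years for the US launch and 6.08 years for the EU launch; the two milestone tables differ from each other by 2.0 years. Under footnote 1 the last entrant of a five-year accrual has at most 5 years, and mean maximum follow-up of about 6.5 to 7.5 years does not reach the 8-year rows of Tables 3 and 4.

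The consequence is an undefined censoring date and possible loss of late person-time in a long-latency safety study. It is not a failed power calculation: the 6-year assumption survives on the documents' figures, though with little margin. The means rest on uniform accrual and ignore death and loss. The EU launch date stands in for France, and nothing can be computed for the UK under footnote 1.

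**What to change.** Adopt one rule throughout.

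1. Keep section 9.2.2 (ten years after the last selected patient, per database) as the single end of follow-up.
2. Change the end of data collection in the section 6 table to September 2038, to match the abstract, interim report 5 and the final report.
3. Rewrite footnote 1 so that the study period follows section 9.2.2 instead of ending ten years after launch.
4. Keep the ten-year minimum in section 9.1, described as potential follow-up unless death or loss to follow-up comes first. Turning it into a maximum would contradict section 9.2.2, under which early entrants are followed for longer than ten years.
5. State the date on which accrual closes in each database. A September 2038 end requires closure by September 2028; if accrual runs to the end of 2028 or is extended, the end date has to move with it.

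The cost is protocol wording and alignment of the milestone dates. If accrual closes by September 2028, the interim and final report dates stay as they are.

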9.1 Study design

This multinational, longitudinal database cohort study will identify patients who are newly treated with efgartigimod and have a diagnostic code for MG (efgartigimod cohort). A patient will be considered an efgartigimod exposed patient if he/she has received at least one (1) dose of efgartigimod.

For each patient entering the efgartigimod cohort, the date of the first efgartigimod exposure in the database (either through an IV infusion or SC injection) will be their index date for the study. Only new users of efgartigimod will be included in this cohort, that is, a patient who receives a first prescription, or first dispensing, or has a first procedure code for efgartigimod during the study period and without a prescription or a dispensing or a procedure code for efgartigimod in the previous 12 months.

A reference cohort will also be selected with a 2:1 ratio to the efgartigimod cohort to provide an overall, real-world assessment of malignancy risk in patients receiving efgartigimod. The reference cohort will consist of patients with a diagnosis code for MG without efgartigimod exposure but is on any other therapy for the treatment of MG during the study period. The index date for each patient in the reference cohort will be assigned as the same index date as the corresponding matched efgartigimod patient.

Identification of patients in the reference cohort will be based on selected matching variables in the patient's history (prior to and including the index date) or within 6 months of the index date. More specifically, within each database, efgartigimod initiators will be matched 2:1 (reference: efgartigimod) by (1) age at index date (+/- 5 years), (2) sex, (3) Charlson Comorbidity Index (CCI)² and (4) duration of prior use of other MG treatment as matching variables prior to and including the index date or within 6 months of the index date.

Patient accrual into the study will begin following the launch of efgartigimod (differs by country), allowing for a lag between actual exposure dates and appearance of the medication record/procedure in each of the data sources, and will continue for up to 5 years via database refreshes (assumed to be annual). To achieve a desired sample size across all databases, a minimum of approximately 1,358 patients will be included in the efgartigimod cohort and 2,716 matched patients in the reference cohort. Accrual of patients into the study cohorts will be monitored annually. Patients will be followed from study entry to at least 10 years following inclusion in the study. If efgartigimod uptake is slower than expected, patient accrual may need to be extended to reach the required sample size.

² CCI is a method of predicting mortality by classifying or weighting comorbid conditions and has been widely utilized by health researchers to measure burden of disease and case mix. Nineteen (19) conditions are included in the index. Each condition is assigned a weight from 1 to 6, based on severity of the disease and estimated 1-year mortality, and these weights from the comorbidities were added to give a singular numeric score which will act as a way of quantifying current health status.

The study will assess the occurrence of any malignancy according to International Classification of Diseases, Tenth Revision (ICD-10) diagnosis codes, which will be grouped according to the ICD-10 classification system (or to the ICD revision valid at time of analysis). More specifically, the first incidence of and time to any malignancy (incidence rate of events of malignancy per PYs exposed in the efgartigimod treated cohort compared to the reference cohort), as well as incidence rate ratio (IRR) will be estimated.

The study will be conducted in validated longitudinal data sources that provide a good representation of the overall healthcare experience in the countries of interest. Analyses will be first conducted independently within each data source to maintain the strengths and unique data features of the individual data sources (e.g., claims data will have highly detailed medication exposure information including days of supply for medications dispensed through outpatient pharmacies; EMR data from clinical settings will have increased outcome validity), and most importantly, to check data integrity (e.g., covariates availability, preliminary study results) across all data sources. A meta-analysis that combines summary results from each country will then be conducted for the final study report after the country-specific analyses are completed.

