9.6 Covariates

This study is designed to describe real-world outcomes associated with the use of efgartigimod. The covariates to be collected include any clinical characteristics, medication use, and medical procedures coded in the databases that could be used to provide a complete description of the cohorts and subpopulations. Baseline covariates observed in the patient’s medical history and other relevant factors prior to the study drug initiation will be assessed.

It is anticipated that not all variables can be collected in the three (3) selected databases; therefore, all covariates will be collected based on data availability. The following list of *a priori* covariates will be evaluated. A more detailed description of relevant covariates and their use in the analysis will be described in the SAP.

1. Cohort identification

- Date(s) of a diagnosis of MG (health care setting) to approximate disease duration (new-/old-onset)

2. Demographic factors

- Gender
- Ethnicity/race (if allowed)
- Patient's age at his/her index date
- Thymoma (with or without thymectomy), if present in database (date, indication, histology)
- [Supplementary variables]
 - Comorbidities
 - CCI will be calculated based on comorbidities identified in the lookback period in the selected databases.
 - Serological testing of MG diagnosis, if available
 - MG Disease severity, if available

3. Lifestyle variables⁴, if available

- Smoking
- Body mass index (BMI)
- Alcohol consumption

4. MG treatment

- Prior and current treatments, e.g.
 - Anticholinesterase agent
 - Corticosteroids
 - Chronic non-steroidal immunosuppressants
 - Monoclonal antibodies
 - Plasmapheresis/plasma exchange
 - IVIg therapy
- Duration of exposure of prior and current treatments, if available
- [Supplementary variables]

⁴ May only be available in EMR database(s) but not claims administration databases.

- Cumulative dose for each line of therapy, if available, and if not, number of distinct concomitant MG treatments (mono-, double or triple therapy)

5. Concomitant treatments

- Type of treatment and duration (for selected concomitant medications)
- [Supplementary variables]
 - Duration of exposure for each treatment
 - Cumulative dose of each treatment, if available

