13.5 Exploratory analysis

The long-term risk of malignancies will be explored within a potential new cohort of MG patients who are treated with other FcRn antagonists, if sufficient patients can be identified for this patient cohort.

The study will also assess time to the first occurrence of malignancy overall and specified by type of malignancy using a Fine and Gray model in order to take into account a potential competitive risk for death and cumulative incidence curves will be provided. The index date will be the first claim of efgartigimod (for the efgartigimod cohort) or other MG treatment (for the reference cohort). The proportional hazards assumption will be checked using statistical tests and graphical diagnostics based on the cumulative sums of residuals. If the assumption is violated, an interaction term with time will be added in the model. The study will also assess the healthcare resource utilization (e.g., number of hospitalisations [including MG-related], ER visits, and MG exacerbations and crises) between the efgartigimod and reference cohorts. This exploratory analysis will be descriptive only; details will be provided in the SAP.

In order to assess the robustness of the results, a Proportional Hazard Model (Cox model) will be performed as a sensitivity analysis with providing cumulative incidence curves.

An exploratory analysis of the CPRD dataset (UK) to identify the extent of recorded MG related information will be performed and if feasible, analysis will be adjusted for disease severity.

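### Section 13.5 gives the reference cohort a different index date from section 9.1, and the matching window in 9.1 reaches past the index date

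*Protocol*

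**What the plan says.** **Time zero.** Protocol section 9.1: "The index date for each patient in the reference cohort will be assigned as the same index date as the corresponding matched efgartigimod patient". Section 13.5, which describes the Fine and Gray model for time to first malignancy (with a Cox model as its sensitivity analysis): "The index date will be the first claim of efgartigimod (for the efgartigimod cohort) or other MG treatment (for the reference cohort").

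**Matching window.** Section 9.1, and the abstract in the same terms, match 2:1 on age at index, sex, CCI and length of past MG therapy. The window for these data is worded "as matching variables prior to and including the index date or within 6 months of the index date". Section 9.6 is narrower: "CCI will be calculated based on comorbidities identified in the lookback period in the selected databases". The footnote to section 8 defines the lookback period as lying before cohort entry.

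**Who is a reference patient.** Section 9.1 describes "patients with a diagnosis code for MG without efgartigimod exposure but is on any other therapy for the treatment of MG during the study period". Footnote 1 to the milestones table in section 6 defines that period: "the overall study period will be from the time of efgartigimod launch in that country and will continue for 10 years". Reference inclusion criterion 2 in section 9.2.1 gives no date on which either condition is judged. Sections 9.2.2 and 13.2 keep reference patients who later start efgartigimod, count their time up to the switch, and censor them there.

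**The concern.** A matched cohort needs one time zero, with eligibility and matching settled from information available on that date. The protocol departs from this in two places and is loosely worded in a third.

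First, if the reference clock starts before the date on which the patient had to be free of malignancy history, the stretch in between cannot contain an event. The efgartigimod clock has no such stretch. The reference hazard is diluted and efgartigimod looks harmful when it is not. Time to first malignancy is a stated objective, and in a safety study a false signal is costly.

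Second, matching on comorbidity or treatment recorded after index conditions on the future, possibly including the consequences of an early cancer. This concerns the primary comparison.

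Third, a reference definition that refers to a ten-year study period does not tell a programmer on which date naivety and current therapy are to be checked.

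**Working it through.** The protocol gives no figure for the size of this problem. Its sizing is the benchmark for what is material, so I reproduced that first.

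**Benchmark (section 11).** Rates 0.042 and 1.3 × 0.042 = 0.0546 per year, 6 years, 2:1, two-sided 5%, effective n = 679. Variance term: 1/(6 × 0.0546) + 1/(2 × 6 × 0.042) = 3.053 + 1.984 = 5.037. Then ln(1.3) × √(679/5.037) = 3.046, and Φ(3.046 − 1.96) = 86.13%, as in Table 4. The study is sized for a rate ratio of 1.3. Nothing below changes the sample size.

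**1. The two index dates.** They cannot generally coincide. Section 9.1 matches on duration of prior MG treatment, so treatment normally began before the matched date, and the earliest claim then falls before that date.

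**2. Size of the clock shift.** Inputs: true ratio 1, rate λ = 0.042 per year (lower planning rate, section 11), follow-up T = 6 years after the matched date. The gap g between the earliest claim and the matched date is not in the protocol; I assume 1 and 3 years. The 3-year case is the longest gap that a 3-year lookback fully covers.

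- Every patient contributing T years: (T + g)/T = 7/6 = 1.17 and 9/6 = 1.50.
- Follow-up ending at first malignancy: mean time E = (1 − e^(−0.252))/0.042 = 5.30 years, and (E + g)/E = 6.30/5.30 = 1.19 and 8.30/5.30 = 1.57.
- Section 13.5 reports hazard ratios, which compare risk sets year by year. Setting the expected Cox score to zero for a 2:1 cohort, with reference hazard 0 up to g and 0.042 afterwards, gives about 1.22 (g = 1) and 2.10 (g = 3), with no competing deaths or other losses.

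**3. The matching window.** History up to and including the index date is already allowed without limit. A further window within 6 months of index adds information only if it lies after index. On that reading, section 9.1 contradicts the lookback-only CCI of section 9.6. For a rough size, suppose matching made event rates fully equal in the first 6 of 72 months. A true ratio of 1.30 would become 1.30 × 11/12 + 1/12 = 1.275. Matching on a summed score would do less than that.

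**4. The reference definition.** Set beside each other, section 9.1 can be read as never exposed during the study period, while 9.2.2 and 13.2 describe patients who may be exposed later and are censored at the switch. Only the second works with an index date assigned by matching, and only the second is written into the primary analysis.

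**The case against.** **The claim-based date is confined to an exploratory analysis.** This stands. The primary ratio in section 13.2 does not use it, so the figures in step 2 must not be read as bias in the primary result. They are also conditional. The section 8 footnote ties the lookback to cohort entry; if cohort entry in 13.5 meant the earliest claim, with history screened before that, the later time would not be event-free by construction. The two sections would still contradict each other.

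**The 6-month clause gives no side.** A backward reading is possible, and several matching variables are anchored at or before index elsewhere. But that reading makes the clause redundant. The protocol says the CCI has nineteen conditions without listing them, so I do not rely on cancer being among them. The sensitivity analysis that drops events in the first 12 months covers the same period, but does not change who was matched.

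**Never-switchers.** A reader might infer from 9.1 that the reference cohort is limited to patients who never switch, and that the primary comparison is therefore biased. Assuming 8 years of follow-up, 5% loss a year and 5% or 10% switching a year, a simulation of such a cohort under no effect gives ratios of 0.84 or 0.70. The documents do not support this: 9.2.2 and 13.2 keep switchers and censor them, which gives about 1.00. The 0.84 and 0.70 also need switching to stop being observed at first cancer; with independent times the ratio is 1.00 even among never-switchers.

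**Re-matching.** Section 9.2.2 says "At each interim analysis, the cohort populations and patient matching will be redefined". A reader might infer that matched sets must be locked. The protocol declares dynamic cohorts openly and leaves detail on switchers to the SAP. No size of harm has been shown, so locking is a preference.

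**Conclusion.** Wrong as written; moderate severity. Sections 9.1 and 13.5 contradict each other on the reference index date. With history screened before the matched date, following 13.5 would give a rate ratio of about 1.17–1.19 (1-year gap) or 1.50–1.57 (3-year gap) under no effect, and a larger hazard ratio in the 3-year case. These rest on the assumed gaps, a constant 42 per 1,000 person-years, 6 years of follow-up and a fully event-free gap. Against a planning ratio of 1.3 they are material, but only for the exploratory time-to-event analysis.

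The 6-month clause does concern the primary analysis. It admits post-index data and conflicts with 9.6, but its likely effect is small: about 0.025 on a ratio of 1.30 under a generous assumption. The study-period wording in 9.1 needs aligning with the censor-at-switch rule, which already governs the primary analysis. The documents do not show material selection or immortal-time bias built into the primary rate ratio.

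**What to change.** 1. Section 13.5: use the matched efgartigimod patient's index date as time zero for the reference cohort, as in 9.1.
2. Abstract and section 9.1: delete the clause allowing matching data within 6 months of the index date, wherever it occurs, so that all matching variables use data on or before that date.
3. Sections 9.1 and 9.2.1: state that reference patients are efgartigimod-naive and on another eligible MG therapy on the matched index date, and that those who later start efgartigimod stay in the reference cohort until the switch, as 9.2.2 and 13.2 already provide.

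The cost is protocol wording and slightly fewer match candidates per initiator. The sample size does not change. The edits are easiest before data collection starts, planned for September 2026.
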